# Multiple Occurrences for Tables:

In all tables about incidence rates of AEs / Infections, if a subject has multiple occurrences of an AE, this subject will be counted only once in the corresponding AE category. If a subject has multiple AEs within a system organ class, s/he will be counted only once for that class. If a subject has multiple severity ratings for an AE while on treatment, s/he is only counted under the maximum rating.

Information pertaining to AEs noted during the study will be listed by subject, including the verbatim term given by the Investigator, the Preferred Term and SOC given by the MedDRA dictionary, start and end date, causality, Grade and relationship to study drug as assessed by the Investigator.

AEs which will be counted for a specific treatment period are those which are treatment emergent. These events are those with an onset after the start of the treatment period, or which were present prior to the start of the treatment period but increased in severity, changed from being not suspected to being suspected of study drug relationship, or developed into SAEs after the start of the treatment period.

# Vital Signs

All vital sign data will be listed by treatment, subject, and visit/time and if ranges are available, abnormalities will be flagged. Summary statistics will be provided by treatment and visit/time.

# **Clinical Laboratory Evaluations**

Abnormalities according to clinically notable criteria will be identified. A by-subject listing of individual subject laboratory data will be generated. Values outside of the clinically notable limits will be flagged. Shift tables describing changes from randomization/enrollment based on the clinical notable criteria will be presented.

Descriptive statistics (mean, SD, minimum, median and maximum) of quantitative laboratory variables, including change from randomization/enrollment, will be generated by visit.

# Other Safety evaluations

# BK-polyoma viremia and nephropathy

The following variables will be analyzed descriptively:

- occurrence of BK-polyoma viremia any time post-transplantation
- occurrence of BK-polyoma virus nephropathy any time post-transplantation

### **EBV and CMV Surveillance**

All quantitative and qualitative EBV and CMV surveillance data (serology and DNA-PCR) will be listed by treatment, subject, and visit/time and if normal ranges are available, abnormalities will be flagged. Summary statistics including mean, SD, minimum, median and maximum as well as change from baseline / previous assessment including shift tables will be provided by subject and treatment by visit/time.

# **Immunogenicity**

Anti-siplizumab antibodies will be determined at specified time points. Immunogenicity data consisting of anti-siplizumab antibodies information will be listed by subject and visit.

#### 12.5.3 **Pharmacokinetics**

Siplizumab serum concentration data will be listed by treatment, subject, and visit/sampling time point. Descriptive summary statistics will be provided by treatment and visit/sampling time point, including the frequency (n, %) of concentrations below the LLOO and reported as zero.

Summary statistics will include mean (arithmetic and geometric), SD, CV (arithmetic and geometric), median, minimum and maximum. Concentrations below LLOQ will be treated as zero in summary statistics and for PK parameter calculations. A geometric mean will not be reported if the dataset includes zero values.

**Table 12-1** Non-compartmental pharmacokinetic parameters

AUClast	The AUC from time zero to the last measurable concentration sampling time (tlast) (mass x time x volume-1)
AUCinf	The AUC from time zero to infinity (mass x time x volume-1)
AUCtau	The AUC calculated to the end of a dosing interval (tau) at steady-state (amount x time x volume-1)
Cmax	The maximum (peak) observed plasma, blood, serum, or other body fluid drug concentration after single dose administration (mass x volume-1)
Tmax	The time to reach maximum (peak) plasma, blood, serum, or other body fluid drug concentration after single dose administration (time)
Lambda_z	Smallest (slowest) disposition (hybrid) rate constant (time-1) may also be used for terminal elimination rate constant (time-1)
T1/2	The elimination half-life associated with the terminal slope $(\lambda z)$ of a semi logarithmic concentration-time curve (time). Use qualifier for other half-lives
CL/F	The total body clearance of drug from the plasma (volume x time-1)
Vz/F	The apparent volume of distribution during terminal phase (associated with λz) (volume)

If data permit, PK parameters will be calculated as described in Section 8.5 and Table 12-1 and will be listed by treatment and subject. Concentrations below the limit of quantification will not be considered for the calculation of PK parameters. Descriptive summary statistics will include mean (arithmetic and geometric), SD, and CV (arithmetic and geometric), median, minimum and maximum. An exception to this is Tmax where median, minimum and maximum will be presented.

Page 84 of 117 Confidential

A dose-independent, model-based analysis of the dose / concentration-exposure relationship should be derived using same the approach. Such analysis may be reported in a separate standalone report

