Preliminary modeling of the limited PK/PD data available in renal transplant patients and T-cell lymphoma patients suggests a strong population effect on the pharmacokinetics of siplizumab (MEDI-507). In renal transplant patients, the apparent PK half-life  $(T_{1/2})$  is 8.5 days. In lymphoma patients, where there is an abundance of CD2+ lymphocytes and CD2 target to which siplizumab can bind, a higher clearance and shorter  $T_{1/2}$  has been estimated of approximately 4.75 days. The primary difference is inflection point concentration at which linear clearance transitions to a more rapid clearance. In T-cell lymphoma patients, this transition occurs at a concentration ~40-fold higher (15 µg/mL) than renal transplant patients (0.35 µg/mL).

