#### 6.2.3 **Investigational Product Dosing Regimen**

The starting dose for siplizumab will be 0.2 mg/kg with escalation to 0.6 mg/kg.

The planned duration of investigational treatment is 5 days. Subjects will receive a total of two doses of siplizumab: pre- or intra-operatively on Day 0 and on Day 4. Subjects may be discontinued from treatment earlier at the discretion of the investigator or upon request of the subject.

Siplizumab dose adjustments and/or interruptions for a given subject are not permitted. The siplizumab infusion rate may be changed in the event of an infusion reaction.

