##### **10.1.1. Extent of Exposure**

Summary statistics of exposure to study drug will be tabulated by treatment arm. The exposure will be summarized using duration and average dosing. Duration of exposure is defined as last

Confidential

Page 18 of 28

dosing date – first dosing date + 40; e.g. 5 PK half-lives. Exposure by average dose is defined as X/Y, where X is the total dose received and Y is planned number of doses to be given.

The duration (days) of study medication administration will be summarized. This will be calculated by subtracting the date of the last administration of study medication from the date of first administration and then adding the dosing interval for Siplizumab, TAC, MMF or CS. In calculating the duration of treatment, days of temporary interruption of study medication for any reason will be included. Further, the frequency of dose changes (including temporary dose interruption) will be presented by reason for the change.

Average daily doses will be presented by treatment. “Zero” will be used for periods of temporary interruption of study medication for any reason.

The number and percentage of subjects who prematurely discontinued study medication will be summarized by reason for discontinuation.

Study treatment errors, including uses outside of what is foreseen in the protocol, will be summarized. AEs as a result of study treatment error will also be summarized.

Extent of exposure data will be presented in a listing.

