### **10.2. Pharmacokinetics and Pharmacodynamics**

#### **10.2.1. Pharmacokinetics**

PK samples will be evaluated for the subjects in PK analysis set at all dose levels.

Sipilizumab concentrations will be determined by a validated ELISA method; the anticipated Lower Limit of Quantification (LLOQ) is 10 ng/mL and concentrations will be expressed in mass per volume units. Concentrations below the LLOQ will be reported as “zero” and missing data will be labeled as such in the Bioanalytical Data Report.

The following PK parameters will be determined using the actual recorded sampling times and non-compartmental method(s):  $C_{max}$ ,  $T_{max}$ , area under the curve (AUC) last,  $AUC_{inf}$ ,  $T_{1/2}$ ,  $V_z/F$ , and  $CL/F$  from the serum concentration-time data.

The linear trapezoidal rule will be used for (AUC) calculation. Regression analysis of the terminal plasma elimination phase for the determination of  $T_{1/2}$  will include at least 3 data points after  $C_{max}$ . If the adjusted  $R^2$  value of the regression analysis of the terminal phase will be less than 0.75, no values will be reported for  $T_{1/2}$ ,  $AUC_{inf}$ , and  $CL$ .

Sipilizumab serum concentration data will be listed by treatment, subject, and visit/sampling time point. Descriptive summary statistics will be provided by treatment and visit/sampling time point, including the frequency (n, %) of concentrations below the LLOQ and reported as zero.

Summary statistics will include mean (arithmetic and geometric), SD, CV (arithmetic and geometric), median, minimum, and maximum. Concentrations below LLOQ will be treated as zero in summary statistics and for PK parameter calculations. A geometric mean will not be reported if the dataset includes zero values.

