**Table 9-1 Non-compartmental pharmacokinetic parameters**

$AUC_{last}$	The AUC from time zero to the last measurable concentration sampling time ( $t_{last}$ ) (mass x time x volume-1)
$AUC_{inf}$	The AUC from time zero to infinity (mass x time x volume-1)
$AUC_{tau}$	The AUC calculated to the end of a dosing interval ( $\tau$ ) at steady-state (amount x time x volume-1)

$C_{max}$	The maximum (peak) observed plasma, blood, serum, or other body fluid drug concentration after single dose administration (mass x volume-1)
$T_{max}$	The time to reach maximum (peak) plasma, blood, serum, or other body fluid drug concentration after single dose administration (time)
$\Lambda_z$	Smallest (slowest) disposition (hybrid) rate constant (time-1) may also be used for terminal elimination rate constant (time-1)
$T_{1/2}$	The elimination half-life associated with the terminal slope ( $\Lambda_z$ ) of a semi logarithmic concentration-time curve (time). Use qualifier for other half-lives
$CL/F$	The total body clearance of drug from the plasma (volume x time-1)
$V_z/F$	The apparent volume of distribution during terminal phase (associated with $\Lambda_z$ ) (volume)

All calculated PK parameters will be listed by treatment and subject. Concentrations below the limit of quantification will not be considered for the calculation of PK parameters. Descriptive summary statistics will include mean (arithmetic and geometric), SD, and CV (arithmetic and geometric), median, minimum, and maximum. An exception to this is  $T_{max}$  where median, minimum and maximum will be presented.

A dose-independent, model-based analysis of the dose/concentration-exposure relationship should be derived using the same approach as the initial model used for expected concentration in the protocol. Such analysis may be reported in a separate standalone report.

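### The adjusted R² rule should also withhold Vz/F and Lambda_z, and a steady-state AUCtau does not fit a two-dose regimen

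*Protocol*

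**What the plan says.** **Parameters to be determined.** Protocol 8.5 and SAP 10.2.1 give the same list: Cmax, Tmax, AUClast, AUCinf, T1/2, Vz/F and CL/F. AUCtau and Lambda_z are not on it.

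**Rejection rule.** Both sections require at least three points after Cmax in the terminal regression. If adjusted R² is below 0.75, "no values will be reported for" T1/2, AUCinf and CL. I read CL here as the CL/F of the list.

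**Parameter tables.** Protocol Table 12-1 and SAP Table 9-1 add two rows, Lambda_z and AUCtau. AUCtau is defined as "The AUC calculated to the end of a dosing interval (tau) at steady-state". Vz/F is "The apparent volume of distribution during terminal phase", tied in the table to the terminal slope.

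**What brings the tables in.** Protocol 12.5.3 says that "PK parameters will be calculated as described in Section 8.5 and Table 12-1", on condition that the data permit it. The SAP text under Table 9-1 has no such condition and lists whatever PK parameters have been calculated.

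**Regimen.** Protocol 6.2.3: "Subjects will receive a total of two doses of siplizumab: pre- or intra-operatively on Day 0 and on Day 4".

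**The concern.** A quality rule on the terminal fit should cover every quantity that depends on that fit. This one stops short. A subject whose slope is judged too poor to give a half-life would, on the wording as it stands, still have a Vz/F in the listing and in the summary statistics. If Lambda_z were listed too, the withheld half-life could be read back from it.

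The AUCtau row is a different kind of problem. Its definition presumes a steady state, and two doses four days apart do not produce one at the half-life the protocol gives for renal transplant patients. A value reported under that name would carry the wrong label.

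Siplizumab PK is an endpoint for the primary objective, and Protocol 1.2 says that the results will inform later dose and regimen selection. The parameter tables should therefore be right, even though nothing is tested.

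**Working it through.** The documents give no figure of their own on this point, so there is none to reproduce.

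**1. What depends on the rejected slope**

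Standard non-compartmental identities, for whichever dose convention is used throughout:

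- T1/2 = ln2 / Lambda_z
- CL/F = Dose / AUCinf
- Vz/F = Dose / (Lambda_z × AUCinf) = (CL/F) / Lambda_z

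| Parameter | In the list to be determined | Depends on the terminal slope | Withheld if adjusted R² < 0.75 |
|---|---|---|---|
| T1/2 | yes | yes | yes |
| AUCinf | yes | yes (extrapolation) | yes |
| CL/F | yes | yes (through AUCinf) | yes |
| Vz/F | yes | yes (slope and AUCinf) | **no** |
| Lambda_z | no, tables only | it is the slope | **no** |

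If Lambda_z is listed, T1/2 = ln2 / Lambda_z returns the rejected value exactly. If Vz/F is listed as well, CL/F = (Vz/F) × Lambda_z returns the withheld clearance.

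**2. How imprecise a rejected slope is**

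With n points, R² = 1 − (1 − adjusted R²)(n − 2)/(n − 1), the slope's t = √[R²(n − 2)/(1 − R²)], and its CV = 1/t. At adjusted R² = 0.75:

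- n = 3: R² = 1 − 0.25 × 1/2 = 0.875; t = √(0.875 × 1/0.125) = 2.65; CV 38%
- n = 5: R² = 1 − 0.25 × 3/4 = 0.8125; t = √(0.8125 × 3/0.1875) = 3.61; CV 28%
- n = 8: R² = 1 − 0.25 × 6/7 = 0.786; t = 4.69; CV 21%

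For a given number of points, fits below the cut-off are less precise than this.

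**3. How far two doses are from steady state**

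Inputs: two doses, interval 4 days (Protocol 6.2.3). Half-lives:

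- 8.5 days in renal transplant patients (Protocol 1.1.4.5)
- 8 days implied by the SAP 10.1.1 exposure rule ("40; e.g. 5 PK half-lives", so 40/5 = 8)
- 4.75 days in lymphoma patients (Protocol 1.1.4.5: "has been estimated of approximately 4.75 days")
- 14–49 h at 0.06 and 0.12 mg/kg (Protocol 1.1.4.6)

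Under linear kinetics, the share of steady-state AUCtau reached in interval n is 1 − 2^(−4n/T1/2), with T1/2 in days. At 8.5 days, the second interval gives 1 − 2^(−8/8.5) = 0.479.

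| Half-life | First interval | Second interval |
|---|---|---|
| 8.5 days | 28% | 48% |
| 8 days | 29% | 50% |
| 4.75 days | 44% | 69% |
| 49 h | 74% | 93% |
| 14 h | 99% | 100% |

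**4. Whether the schedule supports a four-day AUC**

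After the second dose no third dose closes the interval, and Appendix 1 footnote m has samples on Days 7 and 14 but none on Day 8. A second four-day AUC would need interpolation between Days 7 and 14.

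The first interval is well sampled: pre-dose, 1, 3, 6 and 24 h, Days 2 and 3, and Day 4 pre-dose. Its length varies, however. Protocol 6.2.6 fixes the Day 4 infusion between 0800 and 1000 whatever the time of the Day 0 infusion, so the interval can run from about 80 h (Day 0 dose just before midnight) to 106 h (just after midnight at the start of Day 0). For a Day 0 dose at 2000, dose 2 comes at 84–86 h, and a fixed 0–96 h window would include 10–12 h of exposure after it.

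**The case against.** The strongest reply is that the tables are generic definitions and not a list of outputs. AUCtau and Lambda_z are missing from the list to be determined in both documents. The table wording covers any body fluid and describes Cmax and Tmax as after a single dose, which suggests that it was carried over from a template. Protocol 12.5.3 makes calculation conditional on the data, and the SAP lists only what has been calculated. An analyst who has withheld AUCinf and CL would probably not print a Vz/F built from them.

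Much of this stands. A reader might infer that the trial is committed to reporting a steady-state AUCtau, or that a rejected half-life will certainly appear as its Lambda_z. The documents do not go that far. A reader might also infer that a mislabelled AUCtau would distort later dose modelling. That is not supported either: the planned modelling is a population PK/PD analysis, and nothing shows non-compartmental AUCtau feeding it.

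The 48% is also one value in a wide range. Protocol 1.1.4.5 describes parallel linear and Michaelis-Menten clearance, and at the 14–49 h half-lives the second interval would be at or near steady state. Those half-lives come from doses below both used here, although 0.2 mg/kg is only about 1.7-fold above 0.12 mg/kg.

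The Vz/F point is untouched. Vz/F is in the operative list of both documents, and leaving it out of the rule relies on the analyst to notice. For the tables, Protocol 12.5.3 does cite Table 12-1 as a basis for calculation, and the SAP lacks the protocol's condition, so the ambiguity remains.

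**Conclusion.** The concern holds as a minor one.

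- **Vz/F:** holds in full. Following the rule as written reports a parameter derived from a rejected slope and a withheld AUCinf. This rests only on the standard identities.
- **Lambda_z:** holds conditionally. It is not withheld, and it would return the rejected half-life if it were listed.
- **AUCtau:** the definition does not fit the regimen at the stated 8.5-day half-life, where the second interval is at about 48% of steady state. The figure assumes linear kinetics and is indicative: 69% at 4.75 days, and 93% or more at 14–49 h. The documents show an ill-fitting row, not a firm commitment to report it.

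All PK output is descriptive and no hypothesis is tested on it, so the effect is confined to the reported PK parameters. How many subjects would fail the R² rule cannot be judged from the documents.

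**What to change.** 1. In the text of SAP 10.2.1, add Vz/F and Lambda_z to the parameters not reported when adjusted R² is below 0.75, and write CL as CL/F to match the list. Mirror this in Protocol 8.5 at the next amendment.
2. In SAP Table 9-1, and in Protocol Table 12-1 at the same amendment, delete the AUCtau row. Alternatively, redefine it as the partial AUC from the first dose to the actual Day 4 pre-dose sample, using recorded times and no steady-state label. Do not use a fixed 0–96 h window, because it can run past the second dose.

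The cost is one sentence and one table row in the SAP, with matching protocol edits that can wait, since Protocol 13.4.4 requires a written, approved amendment for any change. The samples already scheduled are enough, and dosing, data collection and sample size do not change. If the SAP can no longer be revised before database lock, the same handling can be recorded in the clinical study report as a deviation, as SAP 3 provides.

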#### 12.5.4 **Biomarkers**

All biomarker data (e.g., renal injury markers, cytokine data) will be listed by treatment, subject, and visit/time. Summary statistics will be provided (mean, median, SD, minimum and maximum) by treatment and visit/time.

In the summary tables, the frequency (n, %) of values below the LLOQ and above the upper limit of quantification (ULOQ), respectively, will be included.

In case of censored values (values below the LLOQ and/or values above the ULOQ), the summary statistics (arithmetic mean, SD, geometric mean and CV% of geometric mean) will be calculated as the maximum likelihood estimates using a parametric model for data that can be right censored and left censored assuming the data being normally or log-normally distributed.

#### 12.5.5 **PK/PD Relationships**

The relationship between siplizumab concentration (PK) and PD variables will be explored graphically. Modeling of PK/PD data using a population approach may be performed as appropriate and may be reported in a separate standalone report. The broad principles outlined in the Food and Drug Administration (FDA) Guidance for Industry: PPK will be followed.

### 12.6 **Analysis of Exploratory Endpoints**

### 12.7 **Interim Analyses**

A formal interim analysis (IA) will occur once 50% of subjects assigned to the treatment Cohorts complete their 6-month study assessment. In consideration of the open-label nature of the study design and plan for descriptive statistical analysis, additional ad hoc IA may be performed. Results of the IA will inform decision making on safety, dose escalation and inclusion of additional doses to assure adequate profiling of the siplizumab PK and PD activity.

Details of the IA process and specific analysis will be presented in the SAP.

In addition to the formal planned Interim Analysis, the AE and SAE rates will be monitored on a continuous basis to support the early discontinuation of any treatment arm that is unsafe and/or ineffective according to the Stopping Rules as outlined in Section 9.1.1.

# 12.8 Dosing Decision Data Review

Prior to dose escalation to the next Cohort all available safety, tolerability, PK and PD data from the previous cohort(s) will be reviewed with the Investigators and a joint decision to escalate or terminate the arm will be made.

Dose escalation from one Cohort to the next will be determined at least 28 days following the last investigational product administration in the 4th siplizumab treated subject in each treatment cohort.

The purpose of the Day 28 data review is to confirm progression to the next cohort while the 6-month IA is to support more PK/PD modeling activities necessary to profile longitudinal siplizumab activity for more formal trial design and development decision making.

Results of the Dosing Decision data review will be communicated to the DMC for information, consulting and/or decision purposes as well as to participating investigators for information as deemed appropriate. A separate, cumulative, data package will be provided to the independent DMC as outlined in the DMC charter.

# 12.9 Sample Size Calculation

No formal sample size or power analysis has been performed. A sample size of 8 subjects for each treatment arm was chosen based on practical considerations, including the need to adequately characterize siplizumab PK and PD activity in renal transplant patients in the immediate post-transplant time period while balancing the overall exposure in a mechanistic profiling study.

# 13 Study Conduct

# 13.1 Sponsor Responsibilities

ITB-MED is obligated to conduct the study in accordance with strict ethical principles. ITB-MED will take action to ensure the accuracy and reliability of study data by selecting qualified investigators and sites, by reviewing protocol procedures with the Investigator and relevant study personnel prior to study initiation, by conducting routine monitoring visits and by utilizing robust data management standards.

